3. STUDY DESIGN

3.1 DESCRIPTION OF THE STUDY

[figure not shown]
The study is designed as a multi-site, prospective, 15-month longitudinal, cohort study measuring CSF mHTT in patients with early manifest Stage I or Stage II HD. After completion of the observational period, participants will have the option of receiving the active compound RO7234292 in an OLE study (Study BN40955, ClinicalTrials.gov Identifier NCT03842969), provided they meet eligibility criteria, the data from the ongoing RO7234292 program supports continued development, and subject to approval by the relevant competent authorities and Institutional Review Boards/Ethics Committees (IRBs/ECs).

This study will enroll up to approximately 100 patients at approximately 20 sites. After a 28-day screening period, patients will return to the clinic at baseline and at Months 3, 9, and 15. During these visits, patients will receive clinical, MRI, and Roche HD mobile app assessments; they will also provide CSF and blood samples. Patients who will not enter the OLE study (Study BN40955, ClinicalTrials.gov Identifier NCT03842969) will have a post-observational follow-up visit 2 weeks after the 15-month longitudinal period that may occur by telephone or in the clinic. Early termination visits should take place via clinic visit, where possible. If there is the occurrence of a failed CSF collection procedure due to inadequate establishment of access to the IT space, there may be a second attempt up to 14 days after the original attempt. For this additional visit, local laboratory analysis of coagulation factors (INR and/or PT, aPTT) and platelets must be conducted and the results reviewed within 72 hours prior to performing the LP. In addition, neurological examination, vital signs, and a review of AEs and concomitant medication should occur as part of the safety and tolerability evaluations on the day of LP.

The final study visit will be Study Day 421 (Month 15) for patients who enter the OLE Study (Study BN40955, ClinicalTrials.gov Identifier NCT03842969), and the follow-up visit will be the final study visit for those patients who do not enter the OLE.

[Figure 1](#) presents an overview of the study design, with 1 month defined as one 28-day period. A schedule of activities is provided in [Appendix 1](#).

Figure 1 Study Schema

HD=Huntington's disease.

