4.5.2 Informed Consent Forms and Screening Log

Written informed consent for participation in the study must be obtained before performing any study-related procedures (including screening evaluations). Informed Consent Forms for enrolled patients/study companions and for patients/study companions who are not subsequently enrolled will be maintained at the study site.

All screening evaluations must be completed and reviewed to confirm that patients meet eligibility criteria before enrollment. The investigator will maintain a screening log to record details of all patients screened and to confirm eligibility or record reasons for screening failure, as applicable.

A maximum of one re-screening will be allowed within 8 weeks of the initial screening failure for patients who fail the initial screening (e.g., as a consequence of abnormal laboratory values or general medical status not meeting inclusion or exclusion criteria). If re-screening is required, central CAG repeat length testing from the initial screening does not need to be repeated, and the screening MRI and viral serology from the initial screening may be acceptable as part of the re-screening assessments if performed within 12 weeks of the baseline visit. Participants are not required to re-sign the consent form if they are re-screened.

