Appendix 1 Schedule of Activities

Study Day	Screening Period	Observational Period						Follow-Up (or Early Termination) ^a
	Days -29 to -2	Day -1 to 1 (Baseline)	Day 85 (Month 3)	Day 169 (Month 6)	Day 253 (Month 9)	Day 337 (Month 12)	Day 421 (Month 15)	
Visit Window (days)			±7	±10	±7	±10	±7	
Type of visit	CL	CL	CL	PH	CL	PH	CL	CL or PH
Capacity to consent assessment and informed consent ^b	x							
Demographic data	x							
Medical history and baseline conditions	x	x						
Vital signs ^c	x	x	x		x		x	
Height ^d	x							
Weight ^e	x	x	x		x		x	
Physical examination ^f	x	x	x		x		x	
Neurological examination ^g	x	x	x		x		x	
CAG repeat length ^h	x							
Chemistry, hematology, urinalysis ⁱ	x	x	x		x		x	
Viral serology ^j	x							
Pregnancy test ^k	x		x		x		x	
Coagulation ^l	x	x	x		x		x	
Thyroid panel	x							
ECG (12-lead)	x							

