### **4. STATISTICAL METHODS**

This is longitudinal prospective cohort study and it is exploratory in nature. As such, there is no predefined hypothesis testing, and all analyses will be regarded as exploratory. Where applicable, parameter estimates will be reported together with 95% CI. p-values may still be reported. Basic assumptions of the proposed analyses will be checked, and data transformation (e.g., logarithm transformation) or other analyses could be carried out, if appropriate.

Any patient data listings will be presented for all patients enrolled into the study.

Descriptive summary statistics including but not limited to n, mean, median, SD, range (minimum, maximum) for continuous variables, and counts and percentages for categorical variables will be used to summarize most data by visit.

Study day will be calculated from a reference date, there is no Day 0, as follows:

- Study Day=assessment date – reference date+1,  
if the assessment date is on or after the reference date; or
- Study Day=assessment date – reference date,  
if the assessment date is earlier than the reference date

The reference date for patients who had at least one lumbar puncture (attempted or successful) is the date of the last lumbar puncture for visit Day 1. For patients who did not have a lumbar punctures (LP) the reference date is the date of enrollment in the study (via the interactive voice or web-based response system [IxVRS] system).

For all analysis, where applicable, the value for age, gender and disease stage as reported in the clinical database as well as the value of CAG repeats as measured by the central lab will be used instead of the values coming from IxVRS system.

For all analysis the clinical cutoff date will be applied for all data, i.e. data occurring after the clinical cutoff date will not be included in the analysis.

The fact that patients in this study are matched to the BN40697 study may offer the future opportunity to compare the current observational study against the OLE study. Details of this analysis are not in the scope of this SAP (neither will be reported in the Clinical Study Report [CSR] of Study BN40422) and may be described in a separate document.

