##### **4.5.1 Longitudinal Changes over Time**

The objective of this section is to describe the longitudinal changes over time, to understand disease progression, for all different clinical, digital and PD endpoints, while adjusting for known prognostic factors (such as CAG repeats). Data outside a time window of +- 56 days from the expected scheduled visit will not be used for analysis of summary tables and mean plots by visit.

For the primary and secondary endpoints descriptive tables will be used to summarize the different variables on absolute value, change from baseline and percentage change (where appropriate) from baseline by visit.

For continuous variables, spaghetti plots showing patient profiles and boxplots across time will be presented.

Where the numeric variable indicates an ordinal, rather than continuous, outcome, the analysis will focus on frequency counts and percentages by visit; no other summary statistics will be provided.

In order to model the change from baseline on each individual continuous parameter across time, a mixed-model repeated measures (MMRM) analysis will be applied. This model will include as covariates the baseline parameter, number of CAG repeats, baseline age, CAP, country (as categorical, only for outcome assessments [patient-, observer- and clinician-reported, and performance]) and time (as categorical). Data outside a time window of +- 56 days from the expected scheduled visit will not be used for this analysis. Estimates for the change from baseline based on the MMRM model, at each time-point and computed for the baseline average value of the other baseline covariate, along with corresponding standard error, 95% CI and unadjusted p-value will be presented. Technical details of the MMRM model (e.g. methods for the denominator degree of freedom, variance-covariance matrix, etc.) are given in [Appendix 3](#).

Although confidence intervals and p-values will be reported, no formal hypothesis testing will be considered.

A detailed list of outputs produced for each parameter for describing the longitudinal change over time is described in [Table 2](#).

The procedure that will be used to fit mixed-models in SAS is as follows (with Day 421 as example):

```
proc mixed data=dataname plots=all;
class subjid time Country;
model y-variable=Baseline_y-variable + CAG + CAP + Baseline_Age + Country + time;
repeated time / subject= subjid type=UN;
Estimate "Day 421"
  Intercept 1
  Baseline_y-variable &BASEY
  CAG &CAGBL

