  CAP &CAPBL
  Baseline_Age &AAGE
  time 0 0~1
/ e cl alpha=0.05
run;
```

where &BASEY, &CAGBL &CAPBL and &AAGE will be fixed at the population average at baseline. Time contrast coefficients will be verified with the actual data and

thus the final version of the SAS code may differ from the example above depending on the ordering of the different levels.

Notice that the country variable will only be included when modelling outcome assessments [patient-, observer- and clinician-reported, and performance], pooling country across region (North America -USA plus Canada- vs EU) may be considered in case of convergence problems.

In case a significant number of visits will be delayed beyond the +-56 days, the following additional sensitivity analysis will be conducted, using all data available (irrespective of visit delay).

In order to model the change from baseline on each individual continuous parameter across time, a linear mixed effect model analysis will be applied. The model will include a random intercept and a random slope for the time of assessment (as continuous) . Additionally it will include as fixed effect the time of assessment (as continuous) , the baseline parameter, number of CAG repeats, baseline age, CAP, country (as categorical, only for outcome assessments [patient-, observer- and clinician-reported, and performance]). An unstructured variance covariance matrix will be used for the two random effects (in case of convergence issues, the two random effects will be assumed to be independent).

Least squares means (LSM) estimates for the change from baseline based on the model, at the time of interest, along with corresponding standard error, 95% CI and unadjusted p-value will be presented. The estimate for the fixed effect of time of assessment (population level slope) will be reported along with corresponding 95% CI. For each parameter, all available time-points will be used.

No formal hypothesis testing will be considered and results are presented descriptively with confidence intervals

A detailed list of outputs produced for each parameter for describing the longitudinal change over time is described in [Table 2](#).

The procedure that will be used to fit mixed-models in SAS is as follows with day 421 as example:

```
proc sort data=dataname;
by subjid time;
run;

proc mixed data=dataname plots=all;
class subjid Country;
model y-variable= Baseline_y-variable + Baseline_CAG + Baseline_CAP +
Baseline_Age + Country + time/Solution ;

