##### **4.5.2.2 Model-based Analyses**

In order to model the relationship between a continuous response variable (e.g. the change in cUHDRS) and a main predictor (e.g. change in CSF mHTT) at a given time-point, a linear regression model (LRM) will be used. At each time point only those data from visit occurring  $\pm$  56 days from the scheduled visit will be used.

The full list of analyses which will be considered, together with specifications about additional covariates to account for, is provided in [Table 3](#). Additional analyses, not listed in this SAP, may be conducted to better understand any safety concern which may arise.

Least squares means (LSM) estimates, at each time-point, for the slope of the main predictor (X-variable in [Table 3](#)) along with corresponding standard error, 95% CI and unadjusted p-value will be presented. The estimated effect represents the effect of the main predictor on the response adjusted for all other covariates in the model. Distributional assumptions underlying the model used for analysis will be examined to gain confidence that the model assumptions are reasonable and where needed, sensitivity analyses will be performed.

The procedure that will be used to fit linear regression in SAS is as follows:

```
proc mixed data=dataname plots=all;
class
model y-variable= x-variable + {additional covariates in Table 3} /ddfmi=kr cl;
ods output solutionf=outputname;
run;
```

In addition to [Table 3](#), scatter plots and Spearman correlations will be calculated among all baseline fluid biomarkers at baseline. Similar analyses will be performed for CAG and CAP with baseline fluid biomarkers, baseline CSF mHTT and baseline cUHDRS (including individual components). CAP is defined by the product of (CAG – 33.66) by baseline age.

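### The planned main models analyse visits up to 56 days off schedule at their nominal month with no elapsed-time term, and the continuous-time model is not triggered by delays inside that window

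*SAP*

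**What the plan says.** - **Schedule.** Protocol 3.1 sets out the design "with 1 month defined as one 28-day period". Protocol Appendix 1 places the Month 3, 9 and 15 clinic visits at Days 85, 253 and 421, each with a ±7-day window.
- **Main longitudinal model (SAP 4.5.1).** The MMRM has time as a categorical factor, and "Data outside a time window of +- 56 days from the expected scheduled visit will not be used for this analysis".
- **Association models (SAP 4.5.2.2 and Table 3).** A separate linear regression is fitted at each time point. The data rule, "At each time point only those data from visit occurring" within 56 days of schedule, is the same. No Table 3 row lists time of assessment among its covariates.
- **Continuous-time model (SAP 4.5.1).** A mixed model with a random slope on continuous time uses all data whatever the delay. It is conditional: "In case a significant number of visits will be delayed beyond the +-56 days". No number defines significant. The model is limited to endpoints that change monotonically and describes longitudinal change only.
- **Brain imaging.** SAP 4.5.1.5 mentions an annualised percent change in BSI. Table 2 defines percent change as BSI over baseline volume times 100, and Table 3 uses percent change as the response. The schedule has a scan at screening and none at the baseline visit. After re-screening, Protocol 4.5.2 says the earlier scan "may be acceptable as part of the re-screening assessments if performed within 12 weeks of the baseline visit".
- **Reporting of delay.** SAP 4.2.1 will count COVID-19-related assessments done outside the protocol window. Summarising the length of delay is optional.

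**The concern.** Most outcomes here are expected to drift with time, so a change measured over a longer interval is larger for that reason alone. A window eight times the protocol's (56/7) lets intervals of quite different length enter under one visit label, and the planned main models cannot tell them apart. SAP 4.7 and the SAP change history give COVID-19 delay as the reason for the window, so the departures may run mostly one way.

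The results will be reused. The study aims to describe the rate of CSF mHTT increase, and SAP 4.9 says the patients will serve as external controls for an open-label study. The same section allows interim analyses, and the note to Table 3 gives data up to 9 months as an example. Relative timing error is larger at those visits than at Month 15.

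**Working it through.** **1. Reproduce the schedule.** Scheduled day = 28 × month + 1, which gives 85, 253 and 421, as in Protocol Appendix 1. SAP section 4 states: "Study day will be calculated from a reference date, there is no Day 0". So elapsed days = study day − 1, or 84, 252 and 420 at the nominal visits.

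**2. Elapsed time admitted (nominal ± 56).**

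| Visit | Nominal | Admitted range | Longest/shortest | ±56 as % of nominal | ±7 as % of nominal |
|---|---|---|---|---|---|
| Month 3 | 84 | 28–140 | 5.0 | 66.7% | 8.3% |
| Month 9 | 252 | 196–308 | 1.57 | 22.2% | 2.8% |
| Month 15 | 420 | 364–476 | 1.31 | 13.3% | 1.7% |

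**3. Baselines taken at screening.** SAP 4.4 takes the first available value before lumbar puncture for clinical endpoints measured more than once. That can be a screening value, as early as Day −29. The upper limits then become 140 + 29 = 169, 308 + 29 = 337 and 476 + 29 = 505 days.

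For BSI, an on-time Month 3 scan follows a screening scan by 84 + 2 = 86 to 84 + 29 = 113 days. At the extremes, the interval runs from 28 + 2 = 30 days to 84 + 140 = 224 days. The latter combines a re-screened patient's 12-week-old scan with a visit 56 days late.

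**4. Effect on mean change.** The documents give no distribution of visit timing, so these are assumptions: change proportional to time, a share p of visits late by a mean of d days, and the rest on schedule. Inflation = p × d / nominal days.

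| Visit | p = 20%, d = 20 | p = 40%, d = 35 |
|---|---|---|
| Month 3 | 4/84 = 4.8% | 14/84 = 16.7% |
| Month 9 | 4/252 = 1.6% | 14/252 = 5.6% |
| Month 15 | 4/420 = 1.0% | 14/420 = 3.3% |

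If every visit were late, uniformly by 0 to 56 days (mean 28), the excess would be 28/84 = 33%, 28/252 = 11% and 28/420 = 7%.

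**5. Effect on a predictor slope.** Simulation with assumed inputs: n = 100, mean change −1, true slope −0.30 per SD of predictor, residual SD 1, change proportional to time, 4,000 replicates.

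- *Visits spread evenly over ±56 days:* slope −0.30 and mean −1.00 at all three visits, so no bias. The standard error of the slope rises from 0.101 to 0.111 at Month 3 and stays near 0.10 at Month 15.
- *All visits late, uniformly by 0 to 56 days:* slope −0.40, −0.34 and −0.32 at Months 3, 9 and 15.
- *Timing tied to the predictor (a stress case: 28 days later per SD, capped at ±56):* slope −0.62, −0.40 and −0.37.

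**6. Which remedies work.** Same set-up at Month 3, with 40% of visits 14 to 56 days late:

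- Unadjusted: slope −0.35, mean −1.17.
- Additive elapsed-days covariate: slope still −0.35. Under proportional change, lateness multiplies the slope, and an additive term cannot undo that.
- Predictor-by-time interaction: slope back to −0.30, but its standard error rises from about 0.10 to 0.13.
- Response scaled to the nominal interval: slope −0.30, mean −1.00.
- Deviation from schedule as a covariate, evaluated at the scheduled day: mean back to −1.00, with some loss of precision.

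**The case against.** The strongest reply is that the main question lies at Month 15. Protocol 6.3 frames the primary analysis as change to 15 months, and the Table 3 rows relating baseline mHTT to clinical endpoints and CSF biomarkers use Month 15 only. There the window is ±13% and the assumed inflation about 1% to 3%. A Month 3 change is a response in only three sets of rows: mHTT change against CSF biomarker change, CSF against plasma NfL, and baseline mHTT against BSI. All of this stands. Month 3 still matters for those rows, for the MMRM, and where Month 3 change is the predictor.

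Several stronger readings are tempting, and the documents do not support them:

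- *The plan overstates progression.* The window is two-sided and no timing distribution is given. Net inflation needs visits to be late on average. That is plausible, not established.
- *Timing scatter affects every mHTT regression.* Rows with both variables at baseline contain no follow-up visit.
- *Delays inside 56 days can never be handled.* Once triggered, the continuous-time model uses every visit at its actual time. The gap is that delays of, say, 50 days in every patient would not trigger it, and it never reaches the associations.
- *One added covariate repairs Table 3.* Step 6 shows otherwise for the slope.

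The study is exploratory, without hypothesis testing, and analysis by nominal visit is conventional. That lowers the urgency. The 224-day scan interval is an extreme, and the screening scan is a design feature separate from the window. It is still part of the interval over which BSI accrues.

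**Conclusion.** The point holds for the MMRM and for Table 3 regressions with a follow-up response. They admit elapsed times differing 5-fold at Month 3, 1.57-fold at Month 9 and 1.31-fold at Month 15, with no term for the difference. These ranges follow from the documents alone.

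Bias is conditional. If visits are late on average and change is roughly proportional to time, MMRM mean changes and percent BSI are overstated: by 5% to 17% at Month 3, 2% to 6% at Month 9 and about 1% to 3% at Month 15, under the assumed 20% to 40% of visits late by a mean of 20 to 35 days. Predictor slopes shift only if average timing shifts or timing is related to the predictor. Symmetric scatter costs a little precision, mainly at Month 3. The sponsor should make the change because it is cheap; the Month 15 primary associations are not seriously threatened by average lateness of this size.

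**What to change.** 1. **BSI in Tables 2 and 3.** Use the annualised percent change that SAP 4.5.1.5 already names, or scale to the nominal interval, using the actual dates of the baseline and follow-up scans.
2. **MMRM.** Add the deviation in days from the scheduled day within each visit, and evaluate the estimates at the scheduled day.
3. **Continuous-time mixed model.** Run it as a standing sensitivity analysis for endpoints that meet the SAP's monotonicity condition, replacing the undefined trigger.
4. **Other Table 3 change regressions.** Do not rely on an additive elapsed-days covariate. Use a time-scaled change, or repeat the analysis in visits within the protocol's ±7 days as a sensitivity analysis.

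**Cost.** SAP wording, a derived interval variable and slightly more analysis work. Assessment dates are already needed for study day. The adjusted MMRM means lose some precision, and annualised values are noisier for short scan intervals. The ±7-day analysis drops patients: with 40 of 100 outside the window, the standard error of a slope per SD rises from about 1/√100 = 0.10 to 1/√60 = 0.13, under the residual SD of 1 assumed above.

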2.1 PRIMARY OBJECTIVE

The primary objective of this study is to examine the predictive value of baseline CSF mHTT levels on measures of disease progression using the following endpoints:

- Change from baseline in the following clinical endpoints at 3, 9, and 15 months: composite Unified Huntington's Disease Rating Scale (cUHDRS), Total Functional Capacity Scale (TFC), Total Motor Scale (TMS), Symbol Digit Modalities Test (SDMT), Stroop Word Reading (SWR) Test, and Independence Scale (IS)
- Change from baseline in biomarkers of neuronal injury (e.g., CSF NfL and tau) at 3, 9, and 15 months
- Change from baseline in brain atrophy endpoints (e.g., whole brain volume decline, caudate volume decline) as determined by brain MRI, at 3, 9, and 15 months

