3.3.1 Rationale for Patient Population

Patients with early-stage HD, defined as Stage I or II by Shoulson and Fahn (1979), will be included in this study, as they are expected to show progressive decline in clinical parameters measurable over a \geq 12-month timeframe (Huntington Study Group 1996; Schobel et al. 2017), and because they have measurable abnormalities in the key biomarkers in cross-sectional studies compared to controls and prodromal individuals (e.g., for CSF mHTT [Southwell et al. 2015; Wild et al. 2015]) as well as longitudinal differences on other outcomes (e.g., for NfL, brain atrophy, and clinical endpoints [Byrne et al. 2017]). The population also represents the stage of manifest HD that might be more plausibly reversed or slowed in response to a therapeutic intervention versus more advanced patients with more neurodegeneration present at baseline who experience less longitudinal decline in clinical parameters such as the TFC score (Penney et al. 1990). Since this population overlaps with the population targeted for the upcoming clinical efficacy studies of the RO7234292 development program, the natural history study will provide useful comparative data.

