6.3 PRIMARY ANALYSES

The primary objective of this study is to investigate whether baseline CSF mHTT is a predictor of the change from baseline to 15 months for the following variables:

- Clinical endpoints (cUHDRS, TFC, TMS, SDMT, SWR, and IS)
- CSF and blood biomarkers
- Brain imaging (MRI)

Initially, a linear model will be used to evaluate the association between each response variable (e.g., change from baseline to 15 months in cUHDRS) and baseline CSF mHTT without adjustment for any baseline characteristics.

The same model will then be considered again, adjusting for baseline level of the response variable (e.g., baseline cUHDRS), baseline CSF mHTT levels, CAG, and baseline CAP (the latter defined as the product of age at baseline by [CAG—33.66] (Zhang et al. 2011). A sensitivity analysis to evaluate the impact of additional baseline characteristics (e.g., gender, education level) may be performed.

Other approaches may be used in the case of severe multicollinearity, which would result in model instability.

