### **2.2.1 Primary Endpoints**

The primary objective of this study is to examine the predictive value of baseline cerebrospinal fluid (CSF) mHTT levels on measures of disease progression using the following endpoints:

- Change from baseline in the following clinical endpoints at 3, 9, and 15 months: composite Unified Huntington's Disease Rating Scale (cUHDRS), Total Functional Capacity Scale (TFC), Total Motor Scale (TMS), Symbol Digit Modalities Test (SDMT), Stroop Word Reading (SWR) Test, and Independence Scale (IS)
- Change from baseline in biomarkers of neuronal injury (e.g., CSF neurofilament light chain [NfL] and tau) at 3, 9, and 15 months
- Change from baseline in brain atrophy endpoints (e.g., whole brain volume decline, caudate volume decline) as determined by brain MRI, at 3, 9, and 15 months

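### SAP Table 3 has no model relating baseline CSF mHTT to 15-month change in the Independence Scale or plasma NfL, although the primary analysis names both, and the endpoint lists and analysis sections disagree on visits

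*SAP*

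**What the plan says.** SAP 2.2.1 and Protocol 2.1 state the primary objective, the predictive value of baseline CSF mHTT, and attach endpoints to it. For clinical outcomes SAP 2.2.1 has "Change from baseline in the following clinical endpoints at 3, 9, and 15 months", and its list of six ends with IS. For fluid markers Protocol 2.1 has "Change from baseline in biomarkers of neuronal injury (e.g., CSF NfL and tau) at 3, 9, and 15 months". MRI atrophy is listed at the same three visits.

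Protocol 6.3 describes the analysis. The aim is to "investigate whether baseline CSF mHTT is a predictor of the change from baseline to 15 months for the following variables", and the variables begin with "Clinical endpoints (cUHDRS, TFC, TMS, SDMT, SWR, and IS", followed by "CSF and blood biomarkers" and brain imaging. The protocol synopsis and the synopsis in SAP Appendix 1 repeat this.

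SAP 4.5.2.2 covers the regression models: "The full list of analyses which will be considered, together with specifications about additional covariates to account for, is provided in" Table 3. In that table:

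- Baseline mHTT against change in clinical endpoints is planned at 15 months. The footnote defines clinical endpoints as cUHDRS, TFC, TMS, SDMT and SWR.
- Baseline mHTT against change in CSF biomarkers (NfL, YKL-40, tau) is planned at 15 months.
- Baseline mHTT against the boundary shift integrals (BSI) is planned at 3, 9 and 15 months.
- Plasma NfL appears once, as the response to CSF NfL.

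On IS, SAP 4.5.1.4 promises a continuous-score description and MMRM results, but Table 2 excludes IS from the MMRM.

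**The concern.** The study has no hypothesis test, so the estimated associations are its product. A team that follows Table 3 exactly will report no slope of IS change, or of plasma NfL change, on baseline mHTT. Both belong to the primary analysis as Protocol 6.3 words it. No reason is given for either omission. The same footnote also removes IS from the secondary change-on-change models, although SAP 2.2.2 names it there.

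The disagreement on visits is a separate and milder matter. A reader of the endpoint lists expects an association with baseline mHTT at each visit; a reader of Protocol 6.3 expects one at 15 months. If this is left open, the choice of which earlier-visit associations to report would be made after the data are seen.

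**Working it through.** There is no stated figure to reproduce. The check sets the sections side by side, for models with baseline mHTT as predictor and change as response. The CSF and MRI rows use the examples that the endpoint lists name.

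| Outcome | Protocol 2.1, SAP 2.2.1 | Protocol 6.3, both synopses | SAP Table 3 |
|---|---|---|---|
| cUHDRS, TFC, TMS, SDMT, SWR | 3, 9, 15M | 15M | 15M |
| IS | 3, 9, 15M | 15M | none |
| CSF NfL, tau | 3, 9, 15M | 15M | 15M |
| Plasma NfL | not named | 15M, as blood biomarker | none |
| Whole brain, caudate (MRI) | 3, 9, 15M | 15M | 3, 9, 15M |

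Plasma NfL stands for the blood biomarkers because SAP 4.5.1.2 says that NfL alone among its listed markers is also measured in plasma.

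**Against Protocol 6.3 (15 months).** Named: 6 clinical + 2 CSF + 1 plasma + 2 MRI = 11. In Table 3: 5 + 2 + 0 + 2 = 9. Missing: IS and plasma NfL.

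**Against the endpoint lists (three visits).** Named: (6 + 2 + 2) × 3 = 30. In Table 3: 5 clinical + 2 CSF + 6 MRI = 13. Not modelled: 30 − 13 = 17, made up of

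- five clinical outcomes at 3M and 9M: 5 × 2 = 10;
- IS at three visits: 3;
- NfL and tau at 3M and 9M: 2 × 2 = 4.

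Sixteen of these 17 are 3M or 9M associations. The remaining one is IS at 15M.

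**Do other planned analyses fill the gap?**

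- The MMRM and the all-data sensitivity model in SAP 4.5.1 adjust for the outcome's baseline, CAG, age, CAP and sometimes country. They have no mHTT term for other outcomes.
- The scatter plots in SAP 4.5.2.1 follow Table 3 and give no slope.
- CSF-biomarker change at 3M and 9M is modelled against change in mHTT, with baseline mHTT as a covariate. That coefficient is conditional on mHTT change and is not the reported slope, so it answers a different question.

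**Precision of added 3M and 9M models.** The documents give no variance or effect size, so these are assumptions: standardised variables with residual SD 1, a variance inflation factor of 1.33 for mHTT, and n from 92 (2 × 46, SAP 2.3) to 100.

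- SE = √(1.33/n): 0.120 at n = 92 and 0.115 at n = 100.
- 95% CI half-width = 1.96 × SE: about 0.24 and 0.23.
- With assumed slopes of 0.05, 0.15 and 0.25 at 3M, 9M and 15M, slope/SE at n = 92 is 0.42, 1.25 and 2.08.

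On those assumptions a 3M estimate would say little.

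**The case against.** The best defence is that 15 months is the intended time point. Protocol 6.3 and both synopses say so, and Protocol 3.3.1 chose this population because it is "expected to show progressive decline in clinical parameters measurable over a" period of at least 12 months. That stands. A reader might infer from the count of 17 that most of the primary analysis is missing; the documents do not support this, since 16 of the 17 are earlier-visit associations that Protocol 6.3 does not require. The visit mismatch begins in the protocol, between 2.1 and 6.3.

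Nor are the endpoints left without any estimate. The changes themselves are summarised by visit, and all but IS have an MMRM in Table 2. What is missing is their association with baseline mHTT.

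The SAP states that it supersedes the protocol where specified. This does not rescue IS, because SAP 2.2.1 and 2.2.2 themselves name it. It carries more weight for plasma NfL, which only Protocol 6.3 and the synopses bring in, through blood biomarkers. Even so, the SAP nowhere says that it drops them.

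The study is exploratory, SAP 4.5.3 permits further exploratory analyses, and Table 3's note foresees interim analyses on data up to 9 months. SAP 4.5.2.2 mentions unlisted analyses for safety concerns but does not limit them to that purpose. So the missing models may be run. Permission is not pre-specification, however, and none of these provisions names them.

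IS has 19 discrete levels, and SAP 4.5.1 restricts ordinal outcomes to counts and percentages, so its exclusion may be deliberate. If so, it needs a stated reason, and SAP 4.5.1.4 contradicts it.

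**Conclusion.** The point holds in limited form. Two of the 11 named 15-month associations with baseline mHTT, IS and plasma NfL, have no planned model. The IS omission is the firmer of the two, since it conflicts with the SAP's own endpoint lists as well as with Protocol 6.3. The 3M and 9M question is one of alignment: the endpoint lists and the analysis sections must say the same thing, and only BSI currently has all three visits.

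A reader might go further and conclude that the 15-month regression is inadequate and that a repeated-measures model with an mHTT term is required. The documents do not support that. Any gain would depend on dropout and between-visit correlation, neither of which they give. Such a model is an optional sensitivity analysis.

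The counts rest on the documents alone. Only the precision figures rest on assumptions, and the conclusion does not depend on them.

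**What to change.** 1. Reconcile SAP 4.5.1.4 with Table 2 on whether IS is modelled as continuous. Then add IS to the Table 3 clinical endpoints footnote, which also restores it to the change-on-change models of SAP 2.2.2. If IS is not to be modelled, state the reason.
2. Add a Table 3 row with X = baseline mHTT and Y = change in plasma NfL at 15M. Use the CSF-biomarker covariates, with baseline plasma NfL as the baseline term.
3. State that 15M is the main time point. Then either change the two baseline-mHTT rows (clinical and CSF biomarkers) to 3M, 9M and 15M, with the earlier visits labelled supportive, or bring Protocol 2.1 and SAP 2.2.1 into line with 15M.

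Cost: one footnote, one row and a few cells, using scheduled data and existing code. Steps 1 and 2 add two regressions to the primary question. In the other mHTT rows, IS brings one baseline model and three change-on-change models. The rows with CSF biomarkers as predictor would gain IS too if they share the footnote. Extending the visits in step 3 adds 6 × 2 = 12 clinical and 3 × 2 = 6 CSF regressions (YKL-40 included), 18 in all; aligning the lists to 15M adds none. The downside is more unadjusted exploratory estimates, with those at 3M imprecise.
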